9.1.3 Subject Choice

The subjects are at liberty to withdraw from further infusions at any time.

9.2 OFF STUDY CRITERIA

9.2.1 Withdrawal per subject choice

Subjects are at liberty to withdraw from the protocol at any time. They will continue to receive standard care for their post-transplant complication.

9.2.2 Subject Death

9.2.3 Withdrawal by physician decision

Subjects may be withdrawn from the protocol at any time if the PI deems that the subject will not survive to be evaluable beyond 7 days from transfusion, or that BMSC infusion will complicate the routine management of the recipient. In addition, subjects who are noncompliant with treatment or

*Abbreviated Title: Early BMSC Pilot for Acute GVHD**Version Date: 6/16/2016*

monitoring and those who develop such severe inter-current illness that compromises treatment or evaluation will be taken off study.

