1. INTRODUCTION

1.1 STUDY OBJECTIVES

1.1.1 Primary Objective

Determine the safety and feasibility of adding BMSC infusions to corticosteroid therapy in allogeneic stem cell transplant recipients within 5 days of the diagnosis of *de novo* acute GVHD requiring treatment with systemic corticosteroids.

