9.1.1 Toxicity

Subjects experiencing BMSC infusion reaction as defined in Section 8.2 will receive no further BMSC infusions; subjects experiencing a grade 4 acute infusion reaction or hypersensitivity reaction will receive no further treatments; subjects experiencing a grade 3 acute infusion reaction or hypersensitivity reaction will receive no further treatments if symptoms do not resolve within 2 hours; subjects experiencing a grade 3 acute infusion reaction or hypersensitivity reaction will receive no further treatments if symptoms recur when infusion is restarted. Any subject who encounters a TRSAE will not receive further infusions. Subjects will be followed until off study criteria are met.

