11. BIOSTATISTICAL CONSIDERATIONS

11.1 PRIMARY ENDPOINT

The primary endpoint of this study is:

- The proportion of subjects reaching day +56 without a TRSAE.

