11.2 Secondary Endpoints

Secondary endpoints for this study are:

- Proportions of complete response (CR), partial response (PR), mixed response (MR), no response (NR), and worsening disease (WD) among surviving patients at day +28 and +56 of study (Appendix 2). Need for secondary immunosuppression by day +28 and +56 of study. Steroid dose (prednisone equivalent) at day +28 and +56 of study. Proportion of responses in patients with high and low ST2 levels.

Secondary endpoints will not be used in assessing success or failure of the primary endpoint but are undertaken for descriptive or exploratory research and will be reported accordingly. The duration of treatment limiting toxicity monitoring will be 3 weeks after the last dose of BMSC. The total duration of treatment limiting toxicity monitoring will be 7-11 weeks. Total serious adverse event monitoring will continue until at least 3 weeks after the last dose of BMSC, and subjects experiencing adverse events related to BMSC will be monitored until toxicity resolution or stabilization.

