11.3.2 Sample Size

Let p be the probability of subjects reaching day +56 without a TRSAE. The sample size is determined by testing the null hypothesis $H_0 : p = 75\%$ versus the alternative hypothesis $H_a : p > 75\%$ with a one-sided significant level of 0.05. Based upon our previous phase 1 trial (12-H-0010), the TRSAE rate was 0 out of 10 subjects and we expect 95% subjects would reach day +56 without a TRSAE. Thus a sample size of 23 subjects will achieve 89.5% power to test the above hypotheses using an exact binomial test.

To account for the possibility of non-treatment related drop out, up to 2 additional subjects may be enrolled to replace those subjects that are non-evaluable for the study's primary endpoint for a total accrual of 25 patients. At an accrual rate of 1-2 subjects per month, this study will be completed in 12-18 months.

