11.3.4 Stopping Rules

11.3.4.1 For Mortality

Any death occurring through the follow up period (3 weeks after last BMSC infusion) will halt further accrual irrespective of causality pending IRB review. The study will continue only with IRB determination that the event was not related to study procedures.

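### Removal under 9.2.3 can take a deteriorating subject out of SAE follow-up before day +56, and the plan does not say whether the safety windows and stopping rules still apply

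*Combined protocol and SAP*

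**What the plan says.** The protocol separates stopping infusions (9.1) from leaving the study (9.2). Three grounds for removal stand in 9.2.3, on the off-study side:

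- The PI may withdraw a subject "if the PI deems that the subject will not survive to be evaluable beyond 7 days from transfusion", or where an infusion would complicate routine management. This is discretionary.
- Noncompliant subjects, and "those who develop such severe inter-current illness that compromises treatment or evaluation will be taken off study". This is mandatory.

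Section 9.1.1, on subjects whose infusions are stopped for toxicity, adds: "Subjects will be followed until off study criteria are met".

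Other sections set safety periods by time since the last infusion:

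- Section 8.3 runs the toxicity window to 3 weeks after the last infusion.
- Section 11.2: "Total serious adverse event monitoring will continue until at least 3 weeks after the last dose of BMSC". BMSC-related events are followed until they resolve or stabilise.
- Section 11.3.4.1: "Any death occurring through the follow up period (3 weeks after last BMSC infusion) will halt further accrual irrespective of causality".

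The primary objective (1.1.1) is to "Determine the safety and feasibility of adding BMSC infusions to corticosteroid therapy", and the primary endpoint (11.1) is "The proportion of subjects reaching day +56 without a TRSAE". Sections 3.6, 3.7 and 9.1.2 continue response and survival follow-up for up to 1 year on the parent transplant protocols.

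**The concern.** Taken together, 9.2.3 and 9.1.1 allow a treated subject who is deteriorating to leave the study, and its follow-up, before day +56. For severe intercurrent illness that compromises treatment or evaluation, they appear to require it. Removal then depends on the clinical course that the safety endpoint is meant to capture, and it rests on a judgement made as that course unfolds.

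Sections 8.3, 11.2 and 11.3.4.1 do not mention removed subjects, so site staff cannot tell which instruction governs. Parent-protocol follow-up does not close the gap. It is described for response and survival, whereas a TRSAE needs an SAE to be collected and then judged probably or definitely related to BMSC. At stake are the count behind the primary test, the rule that stops the trial at 3 TRSAE subjects (11.3.4.2), and the certainty that a death after removal triggers the accrual halt.

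**Working it through.** **1. The passages side by side**

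| Section | What it sets | Does it address subjects removed under 9.2.3? |
|---|---|---|
| 9.1.1 | Follow-up until off-study criteria are met | Only by implication: follow-up may end |
| 8.3, 11.2 | Toxicity and SAE monitoring to 3 weeks after the last dose | No |
| 11.3.4.1 | Halt for any death in the same 3 weeks | No |
| 3.6, 3.7, 9.1.2 | Response and survival on parent protocols | Applies after coming off protocol, but not to SAEs |
| 3.4.2.4, 11.3.2, 11.3.3 | Non-evaluability and replacement | No counting rule for removal under 9.2.3 |

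**2. Where a TRSAE could be lost.** An SAE recognised before removal goes to the sponsor at once with a causality assessment (12.4). The endpoint is per subject, so a recorded TRSAE is not undone by removal. Two routes remain: a first TRSAE arising after removal, and an SAE whose attribution rises to probable or definite after removal.

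**3. The plan's own figure.** Inputs from 11.3.2 and 11.3.4.2: n = 23, null p = 0.75, alternative p = 0.95, test "with a one-sided significant level of 0.05", reject if at least 21 of 23 are free of a TRSAE. The formula is P(X ≥ c) = Σ C(n,k) p^k (1−p)^(n−k), summed over k = c to n.

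- At p = 0.75: 0.0376 + 0.0103 + 0.0013 = 0.0492.
- At p = 0.95: 0.2154 + 0.3721 + 0.3074 = 0.8948, against the stated 89.5%. The figure is reproduced.
- A cut-off of 20 gives an error of 0.137, so 21 is the correct cut-off. At most 2 TRSAE subjects are tolerated.

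**4. What one or two losses do**

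- *One loss, subject kept as TRSAE-free.* Two TRSAEs are recorded and one is not. Reported: 21/23, p = 0.049, reject. Full count: 20/23, p = 0.137, do not reject. The third TRSAE subject would have stopped the trial.
- *Two losses, both subjects replaced.* Section 11.3.2 allows up to 2 replacements. Reported: 21/23, p = 0.049. Full count over 25 treated: 21/25 = 84%, p = 0.214. Four TRSAE subjects would have exceeded the limit of 3.

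**5. Effect on the error rate, with assumed loss.** Suppose the true TRSAE rate is 25% and a share h of TRSAEs goes unrecorded and is counted as TRSAE-free. The apparent success probability is 1 − 0.25(1 − h).

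| h (assumed) | Apparent p | Chance of a false success |
|---|---|---|
| 0 | 0.750 | 0.049 |
| 0.1 | 0.775 | 0.082 |
| 0.2 | 0.800 | 0.133 |
| 0.3 | 0.825 | 0.207 |

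**6. Dependence on scoring.** Let m be the number of removed subjects with unobserved outcomes (assumed), removed at random with respect to the outcome.

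| m | One-sided error at p = 0.75 if scored TRSAE-free | Power at p = 0.95 if scored as failures |
|---|---|---|
| 1 | 0.061 | 69.8% |
| 2 | 0.075 | 34.1% |
| 3 | 0.091 | 0 |

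The plan does not say which scoring applies.

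**The case against.** The strongest reply is that 9.2.3 nowhere says safety follow-up ends. The sentence in 9.1.1 concerns subjects stopped for toxicity and does not say follow-up lasts only until then. Sections 8.3, 11.2 and 11.3.4.1 are timed from the last infusion and make no exception for removed subjects, so they can be read as governing. Deaths have a reporting route of their own (12.3.3, within 7 days), and survival continues on the parent protocols. All of this stands. It shows an unreconciled conflict, not a definite cut-off.

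Three stronger readings are tempting, and the documents do not support them.

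- *Deaths after removal escape the mortality halt.* The halt covers any death of any cause within 3 weeks of the last infusion and can be read to include these. The text does not settle it either way.
- *Expected deaths measure the loss.* Six-month survival of 55% to 71% in BMT CTN 0302 (2.2.1) gives, under a constant hazard, 11-week survival of 0.71^(11/26) = 0.865 to 0.55^(11/26) = 0.777. That is 25 × 0.135 = 3.4 to 25 × 0.223 = 5.6 deaths. These are all-cause deaths from other drug combinations. In the phase I trial (2.6.1) there were seven SAEs and one death, and none was attributed to BMSC.
- *The bias must be favourable.* If a removed subject is scored as not having reached day +56, the result is unfavourable, as step 6 shows. Response proportions in 11.2 are in any case restricted to surviving patients.

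The discretionary wording of the expected-death clause also counts against calling every such removal compulsory.

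**Conclusion.** The concern holds as a conflict between 9.1.1 and 9.2.3 on one side and 8.3, 11.2 and 11.3.4.1 on the other. On one permissible reading, SAE collection and attribution stop for the sickest treated subjects before day +56, and no other follow-up replaces them. The loss is limited to TRSAEs that first arise, or are upgraded, after removal.

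The number of such losses cannot be estimated from the documents, and it may be zero. The conclusion is nevertheless fragile. One lost TRSAE subject can move the result from p = 0.137 to p = 0.049, two in replaced subjects can move it from p = 0.214 to p = 0.049, and in either case the stop-at-3 rule does not fire when it should. These cases assume that exactly two TRSAE subjects are recorded and that the removed subjects are either scored as TRSAE-free or replaced. The values of h and m are illustrations, not estimates.

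**What to change.** Reconcile 9.1.1, 9.2.3, 11.2 and 11.3.4.1 with wording to this effect:

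- Removal under 9.2.3 does not end safety follow-up. Every subject who received any BMSC stays under SAE, TRSAE and survival follow-up to the later of day +56 and 3 weeks after the last infusion, unless consent is withdrawn.
- A TRSAE in that period counts for the primary endpoint and for 11.3.4.2, and a death counts for 11.3.4.1, whether or not the subject was removed or replaced.
- Section 11.3 states in advance how a subject who leaves or dies before day +56 without a TRSAE is scored.

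Leave the criteria for stopping infusions, and their discretionary or mandatory wording, as they are. Simply moving the 9.2.3 clauses into 9.1 would not do this. Section 9.1 is written as mandatory cessation, so a discretionary clause would become compulsory.

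The cost is a small amount of extra data collection and possibly a few more recorded events. If replaced subjects stay in the count, a limit of 2 TRSAE subjects still controls the error: 0.0492 at n = 23, 0.0398 at n = 24 and 0.0321 at n = 25. Power is 89.5%, 88.4% and 87.3% respectively.

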9.2.4 Completion of the study

At the conclusion of this study, all surviving subjects will be taken off study or if appropriate enrolled on a follow up study to obtain survival data.

10. DATA MANAGEMENT

10.1 DATA SAFETY

The PI will be responsible for overseeing entry of data into an in-house password protected electronic system and ensuring data accuracy, consistency and timeliness. The principal investigator, associate investigators, Hematology Branch fellows, research nurses and/or a contracted data manager will assist with the data management efforts. Some primary source data on baseline characteristics, BMSC infusions, adverse events, concomitant medications and clinical response will be captured directly on case report forms (CRFs). Data will also be abstracted from Clinical Center progress notes. Laboratory data from NIH will be imported electronically from CRIS into an in-house clinical trial database.

All human subjects personally identifiable information (PII) as defined in accordance to the Health Insurance Portability and Accountability Act, eligibility and consent verification will be recorded. Primary data obtained during the conduct of the protocol will be kept in secure network drives or in approved alternative sites that comply with NIH security standards. Primary and final analyzed data will have identifiers so that research data can be attributed to an individual human subject participant, e.g., study-specific identifying number (SSPIN) or other unique code, or minimum PII required for subject identification. All protocol data will be stored in the NHLBI secured network drive (P drive) with the following security measures: restricted access, password protection and daily off-site back-up.

10.1.1 End of study procedures

Data will be stored in locked cabinets and in a password protected database until it is no longer of scientific value.

10.1.2 Loss or destruction of data

Should we become aware that a major breach in our plan to protect subject confidentiality and trial data has occurred, the IRB will be notified.

10.1.3 Future use of data

Given the research mandate of the NIH, patient data including the results of testing and responses to treatment will be entered into an NIH-authorized and controlled research database. Any future research use will occur only after appropriate human subject protection institutional approval such as prospective NIH IRB review and approval or an exemption from the NIH Office of Human Subjects Research Protections (OHSRP). No identifiable data will be sent outside NIH without IRB notification and an executed MTA or CTA.

Abbreviated Title: Early BMSC Pilot for Acute GVHD

Version Date: 6/16/2016

11. BIOSTATISTICAL CONSIDERATIONS

11.1 PRIMARY ENDPOINT

The primary endpoint of this study is:

- The proportion of subjects reaching day +56 without a TRSAE.

11.2 Secondary Endpoints

Secondary endpoints for this study are:

- Proportions of complete response (CR), partial response (PR), mixed response (MR), no response (NR), and worsening disease (WD) among surviving patients at day +28 and +56 of study (Appendix 2). Need for secondary immunosuppression by day +28 and +56 of study. Steroid dose (prednisone equivalent) at day +28 and +56 of study. Proportion of responses in patients with high and low ST2 levels.

Secondary endpoints will not be used in assessing success or failure of the primary endpoint but are undertaken for descriptive or exploratory research and will be reported accordingly. The duration of treatment limiting toxicity monitoring will be 3 weeks after the last dose of BMSC. The total duration of treatment limiting toxicity monitoring will be 7-11 weeks. Total serious adverse event monitoring will continue until at least 3 weeks after the last dose of BMSC, and subjects experiencing adverse events related to BMSC will be monitored until toxicity resolution or stabilization.

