2. BACKGROUND

2.1 ACUTE GRAFT-VERSUS-HOST DISEASE

Acute GVHD is an inflammatory process that occurs in the majority of patients who receive an allogeneic stem cell transplant. GVHD occurs when host antigen-presenting cells (APC) activate in response to signals from damaged tissue or pathogens. APC present antigens to donor T-lymphocytes, leading to alloreactivity, cytokine release, and increasing tissue destruction, reviewed in¹. Of the more than 7,000 patients who undergo allogeneic stem cell transplant in the US each year², approximately 35-50% will develop grade II-IV acute GVHD despite prophylactic immunosuppression³. GVHD is the second leading cause of death in patients undergoing transplant and it is the leading cause of non-relapse mortality². The standard initial therapy for acute GVHD is high-dose intravenous corticosteroids⁴. The response rate to single-agent corticosteroid therapy, when analyzed in large retrospective reviews, is approximately 50%⁵. In a recent randomized prospective study comparing mycophenolate mofetil plus steroids and steroids alone, the day 56 acute GVHD survival was 50.4% in the steroids alone arm (n=119)⁶. Mortality in patients with acute GVHD is greatest among those who fail to achieve a complete response with initial treatment^{5,7}. Although steroid-resistant acute GVHD can be treated with anti-lymphocyte globulin or a variety of monoclonal antibodies, there is no standard treatment approach and steroid-resistant GVHD has a one year mortality between 50-80%⁸. Acute GVHD usually occurs in the first 100 days of allogeneic stem cell transplant and may involve the skin and/or gastrointestinal tract and/or liver. Following is a summary of the major manifestations of acute GVHD.

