2.2.1 BMT CTN 0302

The first trial was a randomized, four-arm, phase II trial designed to identify the most promising agent to combine with steroids in a phase III trial for upfront treatment of acute GVHD¹⁶. Patients (n=180) were accrued from August 2005 to March 2008 and randomized to receive either etanercept, mycophenolate mofetil (MMF), denileukin difitox, or pentostatin in combination with standard doses of corticosteroids for initial therapy. The proportion of complete responses at day +28 were etanercept (26%), MMF (60%), denileukin difitox (53%), and pentostatin (38%). Day 56 ORR rates were 59%, 78%, 68%, 71% respectively, and OS at 6 months was 59%, 71%, 63%, and 55% respectively. Infection rates and overall toxicities were lower in the etanercept and MMF arms.

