2.2.2 BMT CTN 0802

Based on the results of BMT CTN 0302, a phase III, multi-center randomized trial (BMT CTN 0802) was conducted comparing corticosteroids/placebo to corticosteroids/MMF^{6,17}. Patients received prednisone at 2mg/kg/day with either MMF (1000mg po/IV q8h) or placebo. MMF was continued until day +56 or until steroid discontinuation if sooner. The proportion of GVHD free survival at day +56 after randomization was MMF 59.5% and placebo 50.4% (p=0.16). Overall survival, non-relapse mortality, and incidence of infection were similar in both arms. The study was stopped at a predetermined interim analysis when it was shown that the addition of MMF was unlikely to improve clinical outcomes when compared to steroids alone.

Based on the findings of these recent well-designed multicenter studies, corticosteroid therapy remains the only standard treatment approach for *de novo* acute GVHD requiring systemic therapy.

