3.4.2.4 Missed infusions

Unanticipated logistical challenges including, but not limited to, adverse weather, availability of transportation, or equipment-related delays may occur. Subjects can miss up to four (4) BMSC infusions in total over the course of the treatment protocol and remain enrolled and evaluable for response. If an infusion or series of infusions are missed, the infusion will not be rescheduled and the subject will go on to receive the next scheduled infusion in the treatment course. Subjects missing more than four (>4) BMSC infusions will be removed from the treatment protocol and will not be evaluable for the primary endpoint.

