Appendix 2: Criteria for Response to BMSC

Term	Definition
Complete response (CR)	Resolution of acute GVHD in all involved organs
Partial response (PR)	Organ improvement of at least 1 stage without worsening in any other organ system
Overall response (OR)	CR or PR
Mixed response (MR)	Improvement by at least 1 organ stage in at least 1 evaluable organ with worsening by at least 1 organ stage in at least 1 other organ
Stable disease	The absence of any clinically significant differences (improvement or worsening) sufficient to meet minimal criteria for improvement or deterioration in any evaluable organ
Worsening disease	Deterioration in at least 1 evaluable organ by 1 stage or more
No response	MR or stable disease or worsening disease

Abbreviated Title: Early BMSC Pilot for Acute GVHD**Version Date: 6/16/2016****Appendix 3: Study Calendar for Early BMSC Pilot for Acute GVHD**

Procedure	Protocol Screen												Before and after each infusion +/- 24 hours ^{b, g}	3 weeks after last infusion +/- 7 days	Post Therapy Follow-up ^c
		Day 0 +/- 24 hrs	Week 1	Week 2	Week 3	Day 28 +/- 72 hrs	Week 5	Week 6	Week 7	Day 56 +/- 72 hrs					
History	X														
Physical Exam	X														
Vital signs: BP, HR, RR, Temp, pulse ox	X														
Acute GVHD evaluation	X ^a	X	X	X	X	X	X	X	X	X			X		
Performance Score (KPS)	X														
Labs															
• Pregnancy Test ^c	X														
• CBC/differential	X												X	X	
• Chemistry Panel	X												X	X	
BMSC INFUSION^f													X		
Correlative Research Studies ^g		X										X	X		
Response evaluation ^d						X				X			X		
Adverse events		X	X	X	X	X	X	X	X	X			X	X	
Concomitant Medications		X				X				X			X	X	

^a Tissue biopsy if indicated: See Appendix 1 for GVHD staging. aGVHD evaluation may occur in inpatient or outpatient setting and will occur at minimum on days of BMSC infusion (+/- 24 hours) and at any additional time that is determined necessary by the investigators. aGVHD evaluation will be done at least once weekly for the duration for the first 56 days of treatment.

^b Monitoring according to NIH Clinical Center SOP: [Administration of Products of Cellular Therapy](#)

^c In females of child-bearing potential

^d Response assessment according to condition; response criteria in Appendix 2.

^e Follow up between infusions and after the last BMSC infusion will be based on the subject's condition, as frequently as twice weekly.

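### Section 11.2 takes response proportions among survivors only, which overstates response relative to counting deaths as failures; its response categories also overlap and omit stable disease

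*Combined protocol and SAP*

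**What the plan says.** Section 1.1.2 makes estimating efficacy at the usual GVHD response time points a secondary objective. Section 11.2 puts this into practice as the proportions of CR, PR, MR, NR and WD "among surviving patients at day +28 and +56 of study (Appendix 2". It adds "Proportion of responses in patients with high and low ST2 levels" without giving a denominator, and calls all secondary endpoints descriptive or exploratory.

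No other section changes this. Sections 3.6 and 6.2.1 set the assessment days. Section 3.7 records survival on the same days. Section 11.3.1 promises descriptive statistics on response rates. Appendix 2 has no category for death.

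Appendix 2 defines no response as "MR or stable disease or worsening disease" and worsening disease as "Deterioration in at least 1 evaluable organ by 1 stage or more". It defines stable disease as a category of its own, which the list in 11.2 leaves out.

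**The concern.** **Denominator.** Subjects who die before day +28 or day +56 drop out of the response rate, and they are unlikely to be a random subset. Section 2.1 states: "Mortality in patients with acute GVHD is greatest among those who fail to achieve a complete response with initial treatment". Leaving them out raises the apparent CR and PR rates relative to a rate in which death is a failure.

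The documents' own day +56 reference is in Section 2.2.2: "The proportion of GVHD free survival at day +56 after randomization was MMF 59.5% and placebo 50.4% (p=0.16". Going by its name, a subject who has died cannot be a success on that measure. A survivors-only CR rate is therefore not on the same footing, and readers are likely to set the two side by side.

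Other rules leave the denominator unsettled:
- Section 3.4.2.4 lets subjects with up to four missed infusions "remain enrolled and evaluable for response". For more than four it speaks only of the primary endpoint, and it does not say how infusions not given because of death count.
- Section 11.3.3 replaces subjects with fewer than two doses and makes no exception for early death.

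**Categories.** NR is listed beside two of its own components. Two analysts following 11.2 and Appendix 2 could produce different tables from the same data. This part does not change CR or PR.

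**Working it through.** **Plan's own figure.** The plan gives no figure for the response endpoints. The nearest is the 89.5% power in Section 11.3.2. An exact binomial test with n = 23, at least 21 successes required, p0 = 0.75 and p1 = 0.95 gives a type I error of 0.0492 and power of 0.8948. The figure reproduces, and it does not depend on this point.

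**Inputs.**
- N = 23 evaluable of 25 accrued (Section 3.1.1).
- Responders: assumed 14. Section 2.2.1 reports day 56 overall response of 59% to 78% in the four arms of an upfront-treatment trial, and 0.59 × 23 = 13.6.
- Deaths d: assumed 0 to 4, because the documents give no day +28 or +56 death rate for this population.

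**Denominator effect.** With R responders alive at assessment, the planned rate is R/(N − d). The rate with deaths as failures is R/N. Their ratio is N/(N − d).

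| Deaths d | Factor 23/(23 − d) | 14 responders | Shift from 60.9% | 12 alive in CR |
|---|---|---|---|---|
| 0 | 1.00 | 14/23 = 60.9% | 0 | 12/23 = 52.2% |
| 1 | 1.05 | 14/22 = 63.6% | +2.8 points | 12/22 = 54.5% |
| 2 | 1.10 | 14/21 = 66.7% | +5.8 points | 12/21 = 57.1% |
| 3 | 1.15 | 14/20 = 70.0% | +9.1 points | 12/20 = 60.0% |
| 4 | 1.21 | 14/19 = 73.7% | +12.8 points | 12/19 = 63.2% |

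Exact 95% intervals are 38.5–80.3% for 14/23, 43.0–85.4% for 14/21 and 48.8–90.9% for 14/19. Every shift lies within sampling error.

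**Comparator.** The overstatement is relative to counting deaths as failures. Relative to the same subject having lived, the death of a would-be responder lowers the rate: 15/23 = 65.2% becomes 14/22 = 63.6%.

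**Benchmark (last column).** 0.504 × 23 = 11.6, taken as 12. A regimen about equal to steroids alone would pass the 59.5% of the MMF arm from three deaths on. Without rounding, 50.4% × 23/20 = 58.0% and 50.4% × 23/19 = 61.0%, so the crossing needs four deaths.

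**Plausible d.** Section 2.2.1 gives "OS at 6 months was 59%, 71%, 63%, and 55% respectively", a range of 55% to 71%. Under a constant hazard, S(t) = S6^(t/182.5):
- S6 = 0.71: 5.1% dead by day 28 (1.2 of 23) and 10.0% by day 56 (2.3 of 23).
- S6 = 0.55: 8.8% by day 28 (2.0 of 23) and 16.8% by day 56 (3.9 of 23).

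This suggests 1 to 2 deaths by day +28 and 2 to 4 by day +56. The number may be lower here, because Grade I disease is eligible (Section 5.1.1) and each death halts accrual pending IRB review (Section 11.3.4.1).

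**Replacement.** If two subjects are replaced but kept in the denominator as non-responders, the rate is 14/25 = 56.0% (34.9–75.6%).

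**Categories.** Let SD be stable disease and WD be worsening without improvement. Then NR = MR + SD + WD, and

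CR + PR + MR + NR + WD = 100% + MR + WD.

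Read literally, the worsening definition also covers every MR, and the sum becomes 100% + 2 × MR + WD. Stable disease can be recovered as NR − MR − WD only if MR and WD are kept disjoint.

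**The case against.** The denominator is stated openly, the endpoints are declared descriptive, and survival is recorded on the same days. Anyone given both sets of counts can convert one rate to the other, and Section 11.3.1 does not exclude an all-treated rate. All of this stands, and it limits the weight of the point. But a rate that could be derived is not a planned one, and unlike sampling error this shift always goes upward against the stated comparator.

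The benchmark illustration is open to criticism, and much of that criticism stands. The documents do not define GVHD-free survival, so the comparison rests on its name. Rounding 11.6 up to 12 helps the example. With two deaths the rate stays below 59.5%, and the four-death case uses the worst of four arms. The only death count for this product is one among 10 phase I subjects (Sections 2.5.1 and 2.6.1), which scales to about 2 of 23. No comparison with that trial is planned, and an all-treated rate alone would not make the two fully comparable, since Section 3.4.4.2 allows added systemic therapy. The conclusion does not rest on the illustration.

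Section 3.4.2.4 is about logistical delays, so reading death as a missed infusion is strained. The narrower point remains that the section leaves evaluability for response unstated beyond four missed infusions.

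On categories, an ordinary disjoint reading of MR and WD lets stable disease be found by subtraction. That still leaves NR double-counting both.

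**Conclusion.** The concern holds. As written, 11.2 inflates CR and PR by N/(N − d) relative to counting deaths as failures among all treated: 1.05 to 1.21 for one to four deaths among 23, or 2.8 to 12.8 points at an assumed 14 responders. The effect is zero without deaths. The factor is pure arithmetic; the number of responders, the constant hazard and the transfer of the other trial's survival to this population are assumptions.

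The category overlap follows directly from the text and needs no assumption.

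Both parts concern only descriptive secondary endpoints. They bear on the efficacy estimate named as the secondary objective and leave the primary conclusion untouched. The plan should be changed because the correction is cheap.

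**What to change.** - **Section 11.2, denominator:** use all subjects who received any BMSC for the day +28 and day +56 response proportions, including those replaced or withdrawn. Count death as a failure in the CR and CR + PR rates. Give exact binomial confidence intervals. State the same denominator rule within the high and low ST2 groups. Keep the survivors-only rate as a labelled supplementary figure.
- **Section 11.2 and Appendix 2, categories:** report mutually exclusive lines: CR, PR, MR, stable disease, WD (worsening without improvement in any organ), death before assessment, and alive but not assessed. If NR is kept, use it only as a labelled subtotal of MR, stable disease and WD among assessed subjects, with death outside it.
- **Section 3.4.2.4:** add one sentence saying that evaluability for the primary endpoint does not change the response denominator.

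The cost is wording. Response and survival are already scheduled on both days. Subjects taken off study under Section 9.2 may lack a response assessment; those alive go on the not-assessed line. The reported rate will be somewhat lower if any subject dies, is replaced or is not assessed.
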